5.7 Concomitant and Prohibited Medications

Subjects may not be on any prohibited medications as indicated in the Inclusion/Exclusion Criteria. Please contact the Medical Monitor for any questions related to the subject's current concomitant medication(s). Additional concomitant medications may be permitted on a case-by-case basis at the discretion of the Medical Monitor and the Sponsor.

Lists of permitted and prohibited medications are provided in [Appendix 11.1](#).

5.7.1 Permitted Concomitant Medications

A comprehensive list of permitted medications is shown in [Appendix 11.1.1](#). The list is not all inclusive. Contact the Medical Monitor for any questions related to the subject's current concomitant medication(s). Most of the concomitant medications are allowed if on a stable dose for at least 3 months prior to screening or otherwise specified in [Appendix 11.1.1](#).

- Treatment for hypercholesterolemia (e.g., statins, gemfibrozil) and hyperlipidemia if on a stable dose for ≥ 3 months prior to screening.
- Treatment for hypertension with angiotensin-converting enzyme (ACE) inhibitors, angiotensin receptor blockers, calcium channel blockers, and beta-blockers, alone or in combination with diuretics if on a stable dose for ≥ 2 weeks before screening.
- Inhalers for the treatment of asthma, if the subject has stable, controlled asthma and no changes for ≥ 6 months prior to screening.
- Treatment for diabetes if on a stable dose for ≥ 3 months before screening. Insulin will not be permitted.
- For ADHD treatment, psychostimulants, atomoxetine, guanfacine, and clonidine are allowed, if on a stable dose for ≥ 3 months before screening. Confirmation of ADHD diagnosis will be required.

The stable dose of all concomitant medications permitted in the study **must be maintained** throughout the duration of the study participation.

As needed, the following treatments will also be permitted:

- For sleeping, the following medications are permitted if on a stable dose (dose incrementation is prohibited) for ≥ 4 weeks prior to screening ([Appendix 11.1.1](#)):
 - Hypnotics (e.g., zaleplon and zolpidem).
 - Benzodiazepines: lorazepam (2 mg total daily dose [TDD]), clonazepam (0.5 mg TDD), and flurazepam (30 mg TDD). Benzodiazepines should be taken >12 hours prior to any study visits.

- Trazodone (≤ 150 mg/day) as needed if the subject has been taking the same low dose of trazodone for insomnia for ≥ 3 months.
- Nutritional supplements (e.g., multivitamins, fish oil, melatonin).
- EMLA[®] or other numbing cream for venipuncture.
- Common over-the-counter therapies for minor, transient ailments (e.g., acetaminophen or ibuprofen for headaches, fever, etc.).

All concomitant medications will be recorded in the eCRF.

Subjects must be on a stable dose of 1 study-approved antidepressant medication; a list of these ADTs is provided in [Appendix 11.2](#).

5.7.2 Prohibited Concomitant Medications

A comprehensive list of prohibited medications is provided in [Appendix 11.1.2](#). The list is not all inclusive. Contact the Medical Monitor for any questions related to a subject's current concomitant medication(s).

Prohibited medications should be discontinued for 5 half-lives before baseline. Where a washout of a prohibited medication(s) is required prior to baseline, the tapering rate is at the discretion of the investigator and is to be determined on an individual basis, with consideration to subject state, dose, and known PK of the medication being discontinued. The subject must be consented before any medication tapering is started or any medication is discontinued.

6 STUDY METHODS

The Schedule of Events and Assessments is provided in [Table 1](#), and a detailed schedule of timed assessments (Window) is provided in [Table 2](#).

All subjects who are enrolled and receive the initial administration of SM on Day 1 will be followed according to the protocol regardless of the number of doses of SM taken, unless consent for follow-up is withdrawn. The Sponsor or Sponsor's designee must be notified of all deviations from the protocol clinic visits or procedures, except as noted, and these procedures, if applicable, will be rescheduled or performed at the nearest possible time to the original schedule. AEs should be reported during clinic visits and during at-home contacts. Subjects will also be instructed to call study personnel to report any AEs during the intervals outside the established study contacts and to come to the clinic/or seek medical care if medical evaluation is needed and as the urgency of the situation indicates. For emergencies and other unscheduled visits to a medical facility other than the clinic, medical records will be obtained by the investigator or qualified designee as source data for study follow-up.

Table 1: Schedule of Events and Assessments

Study Period	Screening	Evaluation Period							Safety/ Follow-Up (FPC ^a)
		Seven-Day Treatment Period						EOS/ ET	
	Clinic	Clinic (Baseline)	Home	Clinic	Home	Clinic	Home	Clinic	Home
Visit Number	1	2	-	3	-	4	-	5	
Study Day	-28 to -1	1	2-3	4	5-6	7	8-9	10	12
Window Visit (days)									+2
Sign informed consent	X								
Review eligibility criteria	X	X							
Demographics	X								
Medical history ^b	X								
Confirm MDD diagnosis	X								
Record prior medications	X								
Confirm stable, therapeutic dose of one study-approved ADT	X								
MINI	X								
Physical examination ^c	X	X						X	
Height	X								
Body weight	X	X		X		X		X	
Calculation of body mass index	X								
Vital signs with orthostatic blood pressure and pulse rate ^d	X	X		X		X		X	
12-Lead ECG ^e	X	X		X		X		X	
Blood sample for hematology	X	X				X		X	
Blood sample for chemistry	X	X				X		X	

This document is confidential. It contains proprietary information of Supernus Pharmaceuticals, Inc. Any viewing or disclosure of such information that is not authorized in writing by the Sponsor is strictly prohibited. Such information may be used solely for the purpose of reviewing or performing this study.

Study Period	Screening	Evaluation Period							Safety/ Follow-Up (FPC ^a)
		Seven-Day Treatment Period						EOS/ ET	
	Clinic	Clinic (Baseline)	Home	Clinic	Home	Clinic	Home	Clinic	Home
Visit Number	1	2	-	3	-	4	-	5	
Study Day	-28 to -1	1	2-3	4	5-6	7	8-9	10	12
Window Visit (days)									+2
Blood sample for serology ^f	X								
Blood sample for FSH (postmenopausal females only)	X								
Serum pregnancy test (FOCP only)	X								
Urine sample for urinalysis	X	X				X		X	
Urine sample for urine drug screen and alcohol screen ^g	X	X		X		X		X	
Urine sample for pregnancy test (FOCP only)		X		X		X		X	
HAM-D ₆	X	X	X ^h	X	X ^h	X	X ^h	X	
MADRS	X	X		X		X		X	
CGI-S	X	X		X		X		X	
C-SSRS (Screening/Baseline Version)	X								
C-SSRS (Since Last Visit Version)		X		X		X		X	X
CADSS	X	X				X		X	X
BPRS+	X	X				X		X	X
Review AEs ⁱ		X	X	X	X	X	X	X	X
Review concomitant medications	X	X	X	X	X	X	X	X	X

This document is confidential. It contains proprietary information of Supernus Pharmaceuticals, Inc. Any viewing or disclosure of such information that is not authorized in writing by the Sponsor is strictly prohibited. Such information may be used solely for the purpose of reviewing or performing this study.

Study Period	Screening	Evaluation Period							Safety/ Follow-Up (FPC ^a)
		Seven-Day Treatment Period						EOS/ ET	
	Clinic	Clinic (Baseline)	Home	Clinic	Home	Clinic	Home	Clinic	Home
Visit Number	1	2	-	3	-	4	-	5	
Study Day	-28 to -1	1	2-3	4	5-6	7	8-9	10	12
Window Visit (days)									+2

Blood sample for BDNF ^j		X		X		X		X	
SM administered ^k		X ⁱ		X ⁱ		X ⁱ			
Medication adherence diary ^l	X	X	X	X	X	X	X	X	
ADT ^m	◀								▶

ADT = antidepressant therapy; AE = adverse event; BDNF = brain-derived neurotrophic factor; BPRS+ = Brief Psychiatric Rating Scale Positive Subscale; CADSS = Clinician- Administered Dissociative State Scale; CGI-S = Clinical Global Impression – Severity of Illness; C-SSRS = Columbia Suicide Rating Scale; ECG = electrocardiography; EOS = End of Study; ET = Early Termination; FOCP = females of childbearing potential; FPC = Follow-Up Phone Call; FSH = follicle-stimulating hormone; HAM-D₆ = Hamilton Depression Rating Scale-6 Items; MADRS = Montgomery–Åsberg Depression Rating Scale; MDD = major depressive disorder; MINI = Mini International Neuropsychiatric Review; [REDACTED]; SM = study medication

Note: An attempt will be made to have the same qualified rater administer the same scales (efficacy) throughout the study for each subject. Administration of the HAM-D₆ and MADRS will be performed by 2 different raters.

- The follow-up assessments will be performed through a safety follow-up phone call. The safety follow-up phone call will occur approximately 5 days after the last administration of SM.
- AEs reported during screening will be recorded as part of the subject's medical history.
- A complete physical examination will be performed at screening and baseline visits; a brief physical examination will be performed at EOS/ET.
- Vital signs measurements include orthostatic blood pressure/pulse rate, respiratory rate, and oral temperature. Orthostatic blood pressure and pulse rate should be measured after the subject has been sitting for 5 minutes and again within 3 minutes of subject standing.
- ECGs should be performed prior to blood draws.
- Serology tests include human immunodeficiency 1/2 antigen/antibody, hepatitis B surface antigen, and hepatitis C virus antibody.
- A standard urine drug screen will be performed at screening and point-of-care urine drug screen together with the breathalyzer will be performed at baseline (Day 1) and all post-baseline clinic visits (days 4, 7, and 10).
- On days 2, 3, 5, 6, 8, and 9, the HAM-D₆ questionnaire will be administered remotely by telephone.
- SAEs will be captured from the time of ICF signing, and AEs will be captured following the first administration of SM and continue through the FPC.
- Seven total blood samples will be collected for measurement of BDNF concentrations: 3 pre-dose collections on days 1, 4 and 7; 3 post-dose collections 4 hours after SM administration on days 1, 4, and 7; and 1 collection on Day 10.
- Subjects will take their SM in the clinic.
- Subjects will receive a paper ADT adherence diary at screening and document the day of each dose of their ADT throughout the study. Subjects will bring their ADT adherence

diaries to each clinic visit for review of subject compliance.

m. ADT will not be provided by the Sponsor. Subject's ADT will have started and have been stable for at least 6 weeks prior to screening and will continue through the safety follow-up phone call.

Table 2: Detailed Schedule of Timed Assessments (Window)

Study Day	Clinic Visit Number	Location	Time ^a		HAM-D ₆ ^b	MADRS ^b	CGI-S	BDNF ^c
1	2	Clinic	Pre-dose		X (-60 min)	X (-60 min)	X (-60 min)	X (-60 min)
			1 hour					
			2 hours		X (±30 min)			
			4 hours		X (±30 min)	X (±30 min)		X (±30 min)
			8 hours		X (±30 min)			
2	–	Home	24 hours		X (±2 h) ^e			
3	–	Home	48 hours		X (±2 h) ^f			
4	3	Clinic	Pre-dose		X ^e (-60 min)	X (-60 min)	X (-60 min)	X (-60 min)
			1 hour					
			2 hours		X (±30 min)			
			4 hours		X (±30 min)	X (±30 min)		X (±30 min)
			8 hours		X (±30 min)			
5	–	Home	24 hours		X (±2 h) ^e			
6	–	Home	48 hours		X (±2h) ^f			
7	4	Clinic	Pre-dose		X ^f (-60 min)	X (-60 min)	X (-60 min)	X (-60 min)
			1 hour					
			2 hours		X (±30 min)			
			4 hours		X (±30 min)	X (±30 min)		X (±30 min)
			8 hours		X (±30 min)			
8	–	Home	24 hours		X (±2 h) ^e			
9	–	Home	48 hours		X (±2 h) ^f			
10	5	Clinic	72 hours		X (±2 h) ^g	X (±2 h)	X (±2 h)	X (±60 min)

BDNF = brain-derived neurotrophic factor; CGI-S = Clinical Global Impression – Severity of Illness; h = hours; HAM-D₆ = Hamilton Depression Rating Scale-6 Items;

MADRS = Montgomery–Åsberg Depression Rating Scale; min = minutes; [REDACTED]

a. Time either before (pre-dose) or after SM administration.

b. Administration of the HAM-D₆ and MADRS will be performed preferably by 2 different raters.

c. Seven total blood samples will be collected for measurement of BDNF concentrations: 3 pre-dose collections on days 1, 4 and 7; 3 post-dose collections 4 hours after SM

administration on days 1, 4 and 7; and 1 collection on Day 10.

- e. The HAM-D₆ will be administered remotely on days 2, 5, and 8, approximately 24 hours (± 2 hours) after SM was administered in the clinic on days 1, 4, and 7, respectively.
f. The HAM-D₆ will be administered remotely on days 3, 6, and 9, approximately 48 hours (± 2 hours) after SM was administered in the clinic on days 1, 4, and 7, respectively.
g. The HAM-D₆, MADRS, and CGI-S will be administered on Day 10, approximately 72 hours (± 2 hours) after SM was administered in the clinic on Day 7. The HAM-D₆, MADRS, and CGI-S will be administered prior to any safety assessments.

6.1 Clinic Study Visits and Procedures

6.1.1 Visit 1 – Screening (Day -28 to Day -1)

The following assessments will be conducted:

- Obtain written informed consent
- Confirm MDD diagnosis and conduct the MINI
- Review Inclusion/Exclusion Criteria
- Confirm stable, therapeutic dose of one study-approved ADT
- Record relevant history (social [including alcohol and cannabis consumption], medical, psychiatric, family psychiatric, and neurological)
- Record demographics, height, and body weight
- Record prior and concomitant medications
- Perform a complete physical examination, including the calculation of body mass index
- Record vital signs (orthostatic blood pressure and pulse rate, respiratory rate, and oral temperature)
- Perform 12-lead ECG
- Collect blood sample for:
 - FSH (postmenopausal females only)
 - Serum pregnancy test (FOCP only)
 - Hematology and serum chemistry (non-fasted sample allowed)
 - Serology (i.e., HIV 1/2 Ag/Ab, HBsAg, and HCV Ab)
- Collect urine sample for:
 - Urinalysis
 - Drug and alcohol screen ([Table 3](#))
- Administer efficacy assessments (HAM-D₆, MADRS, and CGI-S)
- Administer safety assessments (C-SSRS [Screening/Baseline Version], CADSS, and BPRS+ scales)
- Provide the subject a paper ADT adherence diary

6.1.2 Visit 2 – Baseline (Day 1)

The assessments listed below will be conducted. See [Table 2](#) for details for efficacy assessments and blood collections for [REDACTED] BDNF.

- Review eligibility criteria
- Record body weight
- Record vital signs (orthostatic blood pressure and pulse rate, respiratory rate, and oral temperature)
- Perform complete physical examination

- Perform 12-lead ECG
 - Collect blood samples for:
 - Hematology and serum chemistry (non-fasted sample allowed)
 - BDNF pre-dose
 - Collect urine sample for:
 - Urine pregnancy test (FOCP only)
 - Urinalysis
 - Drug and alcohol screen
 - Administer efficacy assessments (pre-dose HAM-D₆, MADRS, and CGI-S)
 - Administer safety assessments (C-SSRS [Since Last Visit Version], CADSS, and BPRS+ scales)
 - Review concomitant medications
 - Administer SM
 - Review AEs
 - Administer efficacy assessments following SM administration (HAM-D₆ and MADRS)
 - Collect blood sample for BDNF concentration following SM administration (after efficacy assessments)
 - Review ADT adherence diary

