5.2 Study Medication Administration

SM will be administered orally in the clinic once every 3 days for a 7-day treatment period. SM should be administered in the morning, approximately 3 hours after breakfast.

Subjects will receive a single dose of SPN-820 2400 mg as six 400 mg capsules on days 1, 4, and 7. The capsules will be consumed intact, and splitting the daily dose (e.g., taking part of the daily dose in the morning and the remainder of the daily dose in the evening) is not permitted.

Subjects who cannot tolerate SPN-820 2400 mg should be discontinued from the study at the discretion of the investigator.

Subject will not receive SM on days 2, 3, 5, 6, 8, 9, or 10.

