7.4 Clinical Measurements

7.4.1 Screening and Clinical Safety Laboratory Assessments

All clinical laboratory tests will be performed by a local laboratory as specified in the reference binder.

Details for collecting, handling, and shipping samples (including shipment addresses) will be detailed in a separate clinical laboratory manual. The Schedule of Events and Assessments (Table 1) shows the time points at which blood and urine samples will be collected. Table 3 lists the clinical laboratory tests to be performed.

Table 3: Clinical Laboratory Tests

Category	Parameter
Hematology	Red blood cell count, hemoglobin, hematocrit, platelet count, white blood cell count with differential
Chemistry	Electrolytes: chloride, phosphate, potassium, sodium
	Liver function tests: alkaline phosphatase, aspartate aminotransferase, alanine aminotransferase, total bilirubin, direct bilirubin
	Renal function parameters: blood urea nitrogen, serum creatinine ^a
	Other: glucose, calcium, albumin, total protein, bicarbonate, thyroid-stimulating hormone, free triiodothyronine (T3), free thyroxine (T4), follicle-stimulating hormone (postmenopausal females only)
Serology ^b	HBsAg, HCV Ab, HIV 1/2 Ag/Ab
Urinalysis	Microscopic examination ^c , pH, specific gravity, protein, glucose, ketone, occult blood, white blood cell count, nitrites, bilirubin, urobilinogen
Standard Urine Drug Screen ^d	Amphetamines ^e , barbiturates, benzodiazepines ^e , buprenorphine, cocaine, ecstasy, ethanol, methadone, methamphetamine ^e , methylphenidate ^e , opiates, oxycodone, phencyclidine, propoxyphene, tricyclic antidepressants, tetrahydrocannabinol (cannabinoids)
POC ^f Urine Drug Screen	Amphetamines ^e , barbiturates, benzodiazepines ^e , buprenorphine, cocaine, ecstasy, methadone, methamphetamine ^e , opiates, oxycodone, phencyclidine, propoxyphene, tricyclic antidepressants, tetrahydrocannabinol (cannabinoids)
Breathalyzer ^f	Ethanol
Pregnancy test (FOCP only) ^g	Human chorionic gonadotropin

ADHD = attention-deficit/hyperactivity disorder; FOCP = females of childbearing potential; HBsAg = hepatitis B surface antigen; HCV Ab = hepatitis C antibody; HIV = human immunodeficiency virus 1/2 antigen/antibody; POC = point-of-care

a. Glomerular filtration rate will be calculated using the Chronic Kidney Disease Epidemiology Collaboration equation at screening only.

b. Confirmatory serology testing for positive HIV, hepatitis B and HCV at screening will be performed.

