8.2.3. Clinically Notable Values of Laboratory

Values of laboratory tests are considered clinically notable values (CNV) if they meet the selected criteria in Section 11.3. The number and percentage of subjects with post-baseline CNV will be summarized by overall. For each individual laboratory parameter, the denominator of the percentage includes all subjects who have a non-CNV (or including missing) at baseline and at least one post-baseline assessment (including unscheduled visit) for that parameter. And the numerator of the percentage is the number of subjects who are included in the denominator and

have a CNV at post-baseline for that parameter. A supportive listing of subjects with any CNVs will be provided.

Number and percent of subjects who meet Hy's Law criteria (ALT or AST $>3 \times$ ULN, along with total bilirubin $>2 \times$ ULN and a non-elevated ALP $<2 \times$ ULN, where ULN denotes the upper limit of the normal range) will be summarized.

All laboratory data including repeated values and results from unscheduled visits will be provided in data listings with indication of higher or lower than the reference range of each laboratory test.

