11.3. Criteria for Clinically Notable Laboratory Values

Table 5: Criteria for Clinically Notable Laboratory Values

LBCAT	LBTEST	Sex	LBUNIT	Low	High
Hematology	Basophils		10 ⁹ cell/L	0	0.5
Hematology	Eosinophils		10 ⁹ cell/L	0	1.5
Hematology	Hematocrit (HCT) -Female	Female	LLN or ULN	0.667	1.5
Hematology	Hematocrit (HCT) - Male	Male	LLN or ULN	0.667	1.5
Hematology	Hemoglobin	Female	g/L	80	
Hematology	Hemoglobin Change from Baseline	Female	g/L	20	
Hematology	Hemoglobin	Male	g/L	120	
Hematology	Hemoglobin Change from Baseline	Male	g/L	30	
Hematology	Lymphocytes		10 ⁹ cell/L	0.5	20
Hematology	Monocytes		10 ⁹ cell/L	0	1.2
Hematology	Neutrophils		10 ⁹ cell/L	1.5	
Hematology	Platelet count		10 ⁹ cell/L	75	
Hematology	White blood cells (WBC)		10 ⁹ cell/L	2	100
Serum Chemistry	Alanine aminotransferase (ALT)		ULN		5
Serum Chemistry	Albumin		g/L	20	
Serum Chemistry	Aspartate aminotransferase (AST)		ULN		5
Serum Chemistry	Alkaline Phosphatase (ALP)		ULN		5
Serum Chemistry	Bilirubin		ULN		3
Serum Chemistry	Blood urea nitrogen (BUN)		mg/dL	5	28
Serum Chemistry	Calcium		mmol/L	2	2.9
Serum Chemistry	Chloride		LLN or ULN	0.8	1.2
Serum Chemistry	Creatinine		ULN		3
Serum Chemistry	Glucose - non-fasting		mg/dL	55	180
Serum Chemistry	Glucose - fasting		LLN or ULN	0.7	3
Serum Chemistry	Potassium		mmol/L	3	6
Serum Chemistry	Protein, total		g/L	39	101
Serum Chemistry	Sodium		mmol/L	125	155
Urine	Blood			1+	
Urine	Glucose			1+	
Urine	Protein			2+	

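### SAP Table 5 judges glucose by fasting status, which neither document provides for recording, and its fasting upper limit is looser than its non-fasting one

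*Protocol*

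**What the plan says.** - **Sampling.** Protocol 6.1.2 (Day 1) lists "Hematology and serum chemistry (non-fasted sample allowed", and the visit lists for screening (6.1.1), Day 7 (6.1.4) and Day 10 (6.1.5) carry the same allowance. Glucose belongs to the chemistry panel in Protocol Table 3 ("Other: glucose, calcium, albumin, total protein, bicarbonate"), with no fasting condition attached.
- **Meals.** Protocol 5.2 states: "SM should be administered in the morning, approximately 3 hours after breakfast". No meal rule is given for screening or Day 10.
- **Criteria.** SAP Table 5 (Section 11.3) has a row "Glucose - non-fasting" with limits 55 and 180 mg/dL, and a row "Glucose - fasting" with limits 0.7 and 3, expressed as multiples of the lower and upper limits of normal.
- **Use.** SAP 8.2.3: "Values of laboratory tests are considered clinically notable values (CNV) if they meet the selected criteria in Section 11.3". For the percentage, "the denominator of the percentage includes all subjects who have a non-CNV (or including missing) at baseline", together with at least one post-baseline assessment, unscheduled visits included.
- **Population.** Protocol 5.7.1 permits "Treatment for diabetes if on a stable dose for ≥ 3 months before screening. Insulin will not be permitted". The BMI limit in Protocol 4.2.2 is 40 kg/m².

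**The concern.** The criterion for a notable glucose value turns on whether the sample was fasted. The protocol allows non-fasted draws but does not require them, so both kinds can occur. The schedule of events, the visit lists, Protocol Table 3 and the SAP contain no item for fasting status or time of last meal. SAP 8.2.3 does not say which row applies, or what to do when status is unknown, so a programmer would have to choose without a pre-specified rule.

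The rows also differ in an unexpected way. A meal tends to raise glucose, so a fasting upper limit would be expected to be no higher than the non-fasting one. Here it is much higher. The fasting row is wider on the low side too, but that direction is not odd in itself.

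Laboratory results are a safety endpoint, and subjects on non-insulin diabetes treatment can enrol, so values between the two upper limits are plausible.

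**Working it through.** The plan states no figure to reproduce. The check is threshold arithmetic.

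**Inputs.** The limits come from SAP Table 5. The documents give no LLN or ULN for glucose, so I assume LLN 60-75 mg/dL and ULN 95-140 mg/dL. I read the limits as notable if strictly below the low or above the high figure, because the table prints no operator.

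**Step 1: when is the fasting row wider?**
- High side: 3 x ULN > 180 when ULN > 180/3 = 60 mg/dL.
- Low side: 0.7 x LLN < 55 when LLN < 55/0.7 = 78.6 mg/dL.

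**Step 2: fasting limits over the assumed range.**
- Low: 0.7 x 60 = 42.0; 0.7 x 70 = 49.0; 0.7 x 75 = 52.5. The non-fasting limit is 55.
- High: 3 x 95 = 285; 3 x 100 = 300; 3 x 140 = 420. The non-fasting limit is 180.

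**Step 3: classification with LLN 70 and ULN 100.**

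| Glucose (mg/dL) | Non-fasting row | Fasting row |
|---|---|---|
| 45 | notable | notable |
| 52 | notable | not notable |
| 150 | not notable | not notable |
| 181 | notable | not notable |
| 290 | notable | not notable |
| 301 | notable | notable |

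Any value from 49 up to 55, or above 180 up to 300, is notable or not by label alone.

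**Step 4: where mixed labels can arise.** Baseline is the last non-missing value before the first dose (SAP Table 2), normally Day 1. Protocol 6.1.2 and 6.1.4 list the chemistry draw ahead of dosing, and dosing follows breakfast by about 3 hours, so the Day 1 and Day 7 draws are probably non-fasted. Screening is normally not the baseline and is never post-baseline. That leaves Day 10, early termination (which uses the Day 10 procedures) and unscheduled draws. A fasted sample there, judged by the wider row, can go uncounted.

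Example with ULN 100: a non-fasted baseline of 170 is below 180, so not notable. A fasted Day 10 value of 290 is below 300, so also not notable. The rise is 290 - 170 = 120 mg/dL, and the subject is not counted. Under the 55/180 row the subject would be.

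**Step 5: denominator.** A baseline of 200 is notable under the non-fasting row (subject excluded) and not notable under the fasting row (subject retained). The choice of row therefore also moves the denominator.

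**Step 6: scale.** One subject is 1/50 = 2.0 percentage points, or 1/40 = 2.5. If a share q of 50 subjects had a value in the ambiguous band, the expected number is 50q and the chance of at least one is 1 - (1 - q)^50. The values of q are assumptions:

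| q | Expected subjects | Chance of at least one |
|---|---|---|
| 2% | 1.0 | 64% |
| 5% | 2.5 | 92% |
| 10% | 5.0 | 99.5% |

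These are subjects whose status could depend on the row, not subjects who would be misclassified.

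**The case against.** The other side has several good points.

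- **Fasting status may be collected.** The eCRF was not available, and Protocol 7.4.1 refers collection details to a laboratory manual that was not available either. A reader might infer that the study does not collect fasting status. The documents support only that the protocol and SAP do not provide for it.
- **Errors in both directions.** A reader might infer that a fall in glucose could be counted as a new notable value, for example a fasted baseline of 200 followed by a non-fasted 190 on Day 7. That needs a fasted baseline, which the breakfast instruction makes unlikely. It is not excluded, but it is not the main exposure.
- **A missed rise is not lost.** SAP 8.2.3 marks values outside the reference range in the listings, and SAP 8.2.1 summarises change from baseline. This stands: a value of 290 would be visible there. The shift table helps less, because with ULN 100 both 170 and 290 are classed as high.
- **Limits are the sponsor's choice.** Multiples of LLN and ULN appear elsewhere in Table 5, for example for chloride and creatinine, and no source is given for any limit. This stands as a reason for the sponsor to reconcile the rows. It does not explain why the higher of two values should go uncounted because it was fasted.
- **A natural default exists.** The non-fasting row could be used throughout unless a sample is known to be fasted. That is reasonable, but the SAP does not say it, and it leaves the ordering of the upper limits unresolved.

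**Conclusion.** The point holds as a defect in one descriptive safety summary. Table 5 depends on a label that neither document provides for recording, SAP 8.2.3 has no rule for choosing the row, and the fasting upper limit exceeds the non-fasting one at any ULN above 60 mg/dL. The ordering on the high side would remain a problem even if fasting status turned out to be collected.

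The likely effect is under-counting of fasted samples at Day 10, early termination or unscheduled draws. It is confined to the notable-glucose count, its denominator and the supporting listing of subjects with notable values. The trial is single-arm with no hypotheses, and no efficacy result depends on this count. The exact limits rest on the assumed LLN and ULN; on the high side the conclusion has a wide margin, while on the low side it needs LLN below 78.6 mg/dL. How many subjects would be affected cannot be determined from the documents.

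**What to change.** In SAP Table 5, apply the existing 55/180 mg/dL row to every glucose value, baseline and post-baseline, and delete the fasting row. This needs no new data and removes the ambiguous band. It is a one-row change, best made before database lock. The cost is a few more flags in samples that happened to be fasted: with LLN 70 and ULN 100, those from 49 up to 55 and above 180 up to 300 mg/dL.

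If the sponsor prefers to keep both rows:
1. record fasted yes/no with each chemistry sample;
2. state in SAP 8.2.3 that unknown status uses the non-fasting row;
3. have the sponsor reconcile the two sets of limits.

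In the same edit, align the units: SAP 8.2 calls for SI units in all summaries and listings, whereas the retained glucose limits are in mg/dL.
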